3. **Sleep interaction:** To characterize the degree to which sleep mediates the effect of suvorexant on drug cue reactivity. We hypothesize an indirect effect of suvorexant on drug cue reactivity via sleep, such that attenuation of cocaine cue reactivity (attentional bias, craving) will be greater in those with larger improvements in sleep duration.

*Conceptual Model:
Orexin System Effects on Relapse Risk*

Figure 1. Summary of Conceptual Model

Research Plan

Our group at the University of Texas Center for Neurobehavioral Research on Addiction (CNRA) has developed, utilized, and validated laboratory models of drug relapse, allowing us to examine pharmacotherapeutic and cognitive-behavioral interventions for relapse prevention.

Study design. To accomplish the project aims, we will utilize a mixed-model experimental design, with a between-groups factor of dose (suvorexant vs. placebo) and a within-subjects factor of time. Subjects will receive suvorexant (**10 mg week 1, 20 mg week 2**) or placebo PO, once daily at 10 PM. Medication condition will be double-blind, with urn-randomized assignment to dose condition balanced by gender and severity of cocaine use. A summary of timelines and measures is shown in the Table below.

Mon	Wed	Fri	Mon	Wed	Fri	Mon
1,4,5,6,7	1,2,3,4,5	1,2,3,4,5	1,2,3,4,5,6,7	1,2,3,4,5	1,2,3,4,5	1,2,3,4,5,6,7
Key: (1) Provide medication (MEMS bottle); (2) Compliance data for medication adherence (MEMS, pill count, riboflavin, text message); (3) Side effects data, med check, UA toxicology; (4) Sleep data; (5) stress /anxiety data; (6) acute stressor challenge (cold pressor); (7) Cue reactivity data						

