Stress/Anxiety: VAS-Stress: current stress level is ranked on a 0 – 10 visual analog scale (0 = no stress, 10 = extreme stress) cued by the question “Please rate your current stress level”. We have utilized this measure in previous studies of stress and SUD in our lab^{48,65}.

Medication compliance. Because the medication must be taken in the evening, compliance is a high priority. Accordingly, we will use a four-level approach to measurement of compliance: (1) Medical Event Monitoring System (MEMS, Apex Corp.) bottles, (2) pill counts, (3) riboflavin markers, and (4) text reminders / replies. **Text-based** reminders to take the medication will be enabled via using a HIPAA secure texting service (Talksoft ©), used broadly in medical settings. Participants will be prompted each night at 10 PM to take their medication, and instructed to text back “yes” when they have taken their medication. Compliance-based payment contingencies (M, W, F): $4/4 = 100\%$, $3/4 = 75\%$, $2/4 = 50\%$, etc. These contingencies produce high compliance based on previous work in our laboratory using similar designs, where compliance rates averaged near 90%^{66,67}.

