Subject Payment. The payment schedule is detailed below. Subjects will be paid the medication compliance, study visit bonus, and participation earnings at the end of each experimental day (M, W, F). Subjects will receive an additional bonus (\$50) for completing of the study. Total possible payment for meeting all study requirements and collecting all bonus payments will be \$337.

Medication compliance. \$2 for each metric: 1) Medical Event Monitoring System (MEMS) bottle opening, (2) pill counts (empty bag), (3) positive riboflavin markers, and (4) text reply to reminder. Absence of each will result in payment not being earned for that specific metric. Total possible payment = \$8 per day X 14 study days = **\$112**. **Study visit bonus.** \$10 for on time arrival and providing an alcohol-free breath sample and urine sample. Total possible payment = \$10 per day X 7 visit days = **\$70**.

Participation. Total possible payment = \$15 per day X 7 visit days = **\$105**. **Completion bonus \$50**.

Subject participation requirements. Subjects must take the medication as close as possible to 10:00 PM each evening, and reply “yes” to the medication text prompt (texts will be sent at 15-minute intervals from 9:45 PM to 10:30 PM). On M, W, F over 2 consecutive weeks (see Study Design), subjects will visit the lab at 10 AM. At every visit, they will provide the following: medication update (MEMS bottle), side effects data questionnaire, med check up with nurse, UA fluorescence and toxicology, sleep data (wrist monitor and sleep questionnaire), and stress/anxiety questionnaires. The visit will take approximately 1 hour. In addition, on each Monday (day 1, 7, and 14) subjects will complete: (1) the cold pressor test (with cardiovascular measures and saliva sample for cortisol level), (2) the saccade-based attentional bias test, and (3) the cocaine cue reactivity questionnaire. On these three study days, the visit will take approximately 2 hours.

Data Safety Monitoring Plan

E1. Human Subjects Involvement and Participant Characteristics

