Suvorexant (BELSOMRA) is an orexin receptor antagonist indicated for the treatment of insomnia, characterized by difficulties with sleep onset and sleep maintenance. Recommended dose is 10 mg, 1x per night taken within 30 minutes of going to bed, with at least 7 hours of planned time before awakening. If the 10 mg dose is well tolerated but not optimally effective, it can be increased but not to exceed 20 mg once daily. Medication is taken PO, with dosage in tablets of 5, 10, 15, and 20 mg. Contraindicated in patients with narcolepsy. Precautions include daytime somnolence; dose-related risk of impaired alertness and motor coordination, including impaired driving; patients taking 20 mg should be cautioned against next-day driving; nighttime “sleep-driving” and other complex behaviors while out of bed and/or not fully awake; worsening of depression or suicidal thinking; compromised respiratory function; sleep paralysis, hypnagogic/hypnopompic hallucinations. Risk of the above symptoms increases with use of CNS depressants and alcohol. In obese women (BMI > 30), there is increased risk of exposure-related adverse effects. Belsomra is a schedule-IV compound with mild/modest abuse-potential in the same class as existing sleep medications and anxiolytics. The most common adverse reactions include somnolence and slowed motor coordination. Not recommended for use in patients taking strong CYP3A inhibitors, efficacy may be reduced, or for patients with severe hepatic impairment. Based on animal data, Belsomra may cause fetal harm.

Risks for Behavioral and Psychometric Testing. Behavioral tests are administered via custom written computer programs that track subject’s eye movements. This testing could produce frustration or fatigue if subjects have trouble with acquisition or mastery of the task or concentrating eye gaze for 10-12 minutes. Items on certain psychological/psychiatric questionnaires and interviews might be perceived as personally discomforting to some subjects. While subjects may be uncomfortable reporting these issues, the risks of serious sequelae are extremely low.

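### Dosing is fixed at about 10 PM for everyone, but the protocol's own drug summary ties the dose to bedtime and 7 hours before waking, and nothing visible reconciles the two

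*Combined protocol and SAP*

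**What the plan says.** Three places in the combined protocol and SAP fix the time of dosing:

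- Study design: suvorexant "or placebo PO, once daily at 10 PM".
- Medication compliance (under Measurements): "Participants will be prompted each night at 10 PM to take their medication".
- Subject participation requirements: "Subjects must take the medication as close as possible to 10:00 PM each evening", and "texts will be sent at 15-minute intervals from 9:45 PM to 10:30 PM".

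Section E3 (Potential Risks) summarises recommended use of the drug in insomnia. There the dose is "taken within 30 minutes of going to bed, with at least 7 hours of planned time before awakening". The same paragraph lists reduced alertness and coordination, impaired driving, and complex activity by people who are up but not fully awake.

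The eligibility text (Participants and setting; E1) excludes sleep disorders and sedative medication. It sets no criterion on usual bedtime, usual wake time or night work. The reminders to participants listed in E4 (Other Protections Against Risk) cover food, other medicines and side effects, but not bedtime.

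**The concern.** The dose time is anchored to the clock in one part of the protocol and to going to bed in another. A participant who usually goes to bed late, or gets up very early, is eligible under the visible criteria. By doing what Subject participation requirements says they must do, that participant is dosed outside the conditions that E3 describes.

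The main stake is safety. E3 itself names the risks of being up or driving while affected. The impairment checks in E4, and in E10 under Safety of Research Participants Outside of the Research Site, are made at laboratory visits, and visits are at 10 AM. The visible text does not address a participant who is still up after the evening dose.

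There is a smaller scientific stake. Sleep duration is the mediator in Aim 3. The interval from dose to sleep is neither controlled nor listed as recorded, and Data Analyses does not mention it. The urn randomization balances gender and severity of cocaine use, not sleep timing.

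**Working it through.** No sample size, power or error rate is involved. The check is clock arithmetic, plus the payment figures, because payment bears on how strong the incentive is.

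**1. Payment figures (Subject Payment).** Four metrics at $2 give 4 × 2 = $8 per day, and 8 × 14 = $112. Adding 10 × 7 = $70, 15 × 7 = $105 and the $50 completion bonus gives 112 + 70 + 105 + 50 = $337. Both stated totals reproduce. The text reply is worth 2 × 14 = $28, which is 28/112 = 25% of the compliance payment and 28/337 = 8.3% of the total.

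**2. When a clock-time dose fits the E3 description.** Inputs: prompts at 9:45 to 10:30 PM and a nominal dose at 10 PM (Subject participation requirements); 30 minutes and 7 hours (E3). Latest bedtime = dose time + 30 minutes. Earliest planned waking = dose time + 7 hours.

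| Dose taken | Bedtime no later than | Planned waking no earlier than |
|---|---|---|
| 9:45 PM | 10:15 PM | 4:45 AM |
| 10:00 PM | 10:30 PM | 5:00 AM |
| 10:30 PM | 11:00 PM | 5:30 AM |

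This counts the 7 hours from the dose. Counted instead from a bedtime 30 minutes after the dose, the waking limits move to 5:15, 5:30 and 6:00 AM.

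**3. Illustrative bedtimes.** These are assumptions, since the documents give none. Excess over the window = (bedtime − 10 PM) − 30 minutes.

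- 11 PM: 60 − 30 = 30 minutes
- Midnight: 120 − 30 = 90 minutes
- 1 AM: 180 − 30 = 150 minutes
- 2 AM: 240 − 30 = 210 minutes

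If the dose is taken at the last prompt, 10:30 PM, each excess falls by 30 minutes and an 11 PM bedtime just fits.

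**4. Interval from dose to testing.** From 10 PM to the 10 AM visit is 12 hours. Over the prompt window it is 12.25 hours (9:45 PM) down to 11.5 hours (10:30 PM). The visit time itself therefore does not force waking within 7 hours of the dose.

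**The case against.** The best defence is that E3 is not a study rule. It summarises recommended use in insomnia within a section on risk, whereas the 10 PM time is a design choice with a real merit: it holds the interval from dose to cue-reactivity testing near 12 hours for everyone. That stands. It makes this an unreconciled gap, not a contradiction for every participant. It does not close the gap, because the protocol never says whether the E3 conditions apply to its own participants.

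It is also fair that written and verbal medication information goes to all participants and that the consent pages are not visible. A bedtime instruction may exist there. Other safeguards count too: sleep disorders and sedatives are excluded, evening alcohol is restricted, participants who appear impaired at a visit are kept until they recover, and E4 expects driving hazards to be rare because most participants use public transport. None of these covers a participant awake at home after the dose.

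Two stronger readings are tempting, and the documents support neither.

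- *Participants are paid to dose at 10 PM regardless of bedtime.* The paid metrics are "Medical Event Monitoring System (MEMS) bottle opening, (2) pill counts (empty bag), (3) positive riboflavin markers, and (4) text reply to reminder", and "Absence of each will result in payment not being earned for that specific metric". None carries a clock time or deadline. Only the reply is linked to the evening prompts, and participants send it once the dose is taken. A late dose with a late reply breaks no stated payment rule.
- *Variable bedtimes weaken the drug's effect on sleep and so undermine Aim 3.* The documents give no data on onset, duration or response by timing. Both arms follow the same rule, so bedtimes are balanced in expectation. With 30 completers a chance imbalance is possible, but a loss of effect is conjecture.

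**Conclusion.** The gap is real and should be closed. The study requires dosing at about 10 PM for all, while its own drug summary sets conditions that a 10 PM dose meets only with a bedtime by 10:30 PM and planned waking at 5 AM or later. The early-riser part is correspondingly narrow: it concerns planned waking before about 5 AM, or before 4:45 to 5:30 AM across the prompt window.

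The number of participants affected cannot be estimated. The protocol's background on sleep in addiction describes disrupted architecture and reduced total sleep, not late bedtimes or early rising. That late sleepers would be enrolled is an inference from the lack of any criterion excluding them. The conclusion also assumes that the removed consent pages do not already deal with bedtime.

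This is a point of participant safety and internal consistency. It does not show that the Aim 1 comparison or the Aim 3 mediation result would be biased.

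**What to change.** Reconcile Study design, Medication compliance and Subject participation requirements with the bedtime and 7-hour conditions in E3. Which governs is for the medical director, and no dosing rule is proposed here. That decision should take into account that a fixed clock time keeps the dose-to-test interval near 12 hours, and that individual dosing times would make it vary and need prompts set per participant.

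Carry the outcome into three places: the screening questions, the participant information described in E4, and the wording of the prompts. At the same time align the two prompt descriptions, since one section gives a 10 PM prompt and another gives prompts every 15 minutes from 9:45 to 10:30 PM.

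For the analysis, first confirm whether the MEMS bottles record opening times and whether the wrist monitor exports sleep onset. The protocol names only total sleep and deep sleep duration as the monitor's primary outputs, and it describes MEMS by bottle opening without mentioning a time. If both timestamps exist, derive the nightly dose-to-sleep interval and report it by arm alongside the Aim 3 results. If not, omit it.

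The cost is protocol and prompt wording and a few screening questions, plus one derived variable if the timestamps are available. The fixed 10 PM time need not be given up for the text to be made consistent, and the payment scheme needs no redesign on this ground.

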Participants and setting. The study will test 30 current cocaine users (enroll 45 to complete 30), 19 to 55 years old, who meet current DSM-5 criteria for cocaine use disorder (CUD) of at least moderate severity (≥ 4 symptoms). Subjects meeting criteria for substance use disorders other than cocaine, marijuana, or nicotine will be excluded. Notably, because the study medication (suvorexant) is contraindicated with alcohol use, we will exclude subjects with alcohol use disorders (via screening at intake). We will also exclude those individuals who are drinking > 10 alcoholic drinks per week (NIAAA criteria problem drinking = at least 14 drinks per week), and who are unwilling to stop using alcohol in the evening for the two weeks of the study. We will exclude those who report binge drinking (NIAAA criteria = in < 2.5 hours, 5 drinks for men, 4 drinks for women).

Other exclusion criteria will include significant and unstable medical/ psychiatric disorders which might make participation hazardous; acute or chronic health conditions; and concomitant medication use contraindicated with the study medication (suvorexant). This will be accomplished via full medical evaluation at intake by [name], M.D., CNRA Medical Director. The study will be conducted at the Neurobehavioral Research Laboratory at the CNRA, directed by [name]. Recruitment strategies will include local advertising in print media, public service announcements on radio, and referrals to CNRA in the Houston metropolitan area. Based on previous and current CNRA recruitment rates of participants with CUD, we expect to enroll 3-4 participants per month to meet recruitment goals.

Measurements

Cue reactivity: Attention bias (AB) task is a saccade-based eye-tracking measurement, developed by [name] to assess attentional bias to drug cues⁴⁸. Eye movements (saccades) have advantages over other variables because they are directly observable, ecologically valid, and typically stable across repeated measures^{49,50}. AB measures utilizing eye movements have produced moderate to robust effects for a broad class abused substances⁵¹⁻⁵³, including cocaine^{34,48,54}. Using our drug specific anti-saccade task, the between-group effect size for anti-saccade error rates in the presence of cocaine cues was large: CUD vs. control Cohen's $d_{av} = 0.6$ ⁴⁸.

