The study will test 30 current cocaine users (enroll 45 to complete 30), 19 to 55 years old, who meet current DSM-5 criteria for cocaine use disorder (CUD) of at least moderate severity (≥ 4 symptoms). Subjects meeting criteria for substance use disorders other than cocaine, marijuana, or nicotine will be excluded. Notably, because the study medication (suvorexant) is contraindicated with alcohol use, we will exclude subjects with alcohol use disorders (via screening at intake). We will also exclude those individuals who are drinking > 7 alcoholic drinks per week, and who are unwilling to stop using alcohol in the evening for the two weeks of the study. Other exclusion criteria will include significant and unstable medical/ psychiatric disorders which might make participation hazardous; acute or chronic health conditions; and concomitant medication use contraindicated with suvorexant (e.g., medications with sedative properties). This will be accomplished via full medical evaluation at intake by [name], M.D., CNRA Medical Director. The study will be conducted at the Neurobehavioral Research Laboratory at the CNRA, directed by [name]. Recruitment strategies will include local advertising in print media, public service announcements on radio, and referrals to CNRA in the Houston metropolitan area. Based on previous and current recruitment rates of cocaine treatment-seeking men and women for studies at the CNRA, we expect to enroll 3-4 participants per month to meet recruitment goals. Subjects will be required to participate for 2 days (intake, screening) + 2 weeks (formal experimental study), coming to the CNRA lab M, W, F.

Research data will be collected at scheduled time points during intake, baseline, experimental conditions, and end-of-study. Urine assays will assess recent cocaine use as urine benzoylecgonine < 300 ng/mL confirmation.

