Exclusion criteria will include: (1) current DSM-IV diagnosis of any psychoactive substance dependence other than cocaine, marijuana, or nicotine; (2) have a DSM-IV axis I psychiatric disorder or neurological disease or disorder requiring ongoing treatment and/or making study participation unsafe; (3) significant current suicidal or homicidal ideation; (4) medical conditions contraindicating administration of suvorexant (e.g., severe pulmonary disease, severe cardiovascular disease or clinically abnormal EEG, severe liver or kidney disease, seizure disorder, or sleep disorder – particularly narcolepsy); (5) taking medications known to have significant drug interactions with the study medication(s) (e.g., MAO inhibitors, anticonvulsants, haloperidol, phenothiazines, anesthetics, and all sedatives); (6) currently or recently (last 3 months) treated for substance use [other than cocaine or nicotine] or another psychiatric condition; (7) conditions of probation or parole requiring reports of drug use to officers of the court; (8) impending incarceration; (9) pregnant or nursing for female patients; (10) inability to read, write, or speak English [required for lab tasks and psychometric scales]; (11) unwillingness to sign a written informed consent form; (12) subjects with alcohol use disorders or are drinking > 7 alcoholic drinks per week. All subjects who are excluded will be given referral information to other local treatment programs.

E2. Sources of Materials.

We will obtain information about subjects from structured interview evaluations, physical examinations, self-report measures, and computerized behavioral tasks. This information will be collected at specified time points during the study phases of intake, baseline assessment, experimental testing, and end-of-study. The biological specimens obtained from all subjects will include urine, saliva for cortisol assessment, and breath samples for alcohol detection. Individuals who volunteer to participate will be assigned a subject number (e.g., 10500), under which all information collected will be filed. All materials will be obtained for the specific purposes of this research.

E3. Potential Risks

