Risks for Cold Pressor Test. Individuals with cardiovascular disorders and neurological disorders should not participate. This information will be obtained during medical screening. Due to individual variation in pain and cold sensitivity, for some subjects the cold water may become too painful to sustain immersion for 90 seconds. There are no lasting effects from placing the hand and wrist in ice water (0° Celsius) for 90 seconds.

Risks for Physical Examination. There is a slight risk of bruising and infection in the blood draw procedures. This draw and the intake screening and physical exam are part of the CNRA General Evaluation protocol, and are approved under protocol HSC-MS-05-0322 and detailed therein.

E4. Adequacy of Protection Against Risks

Procedures to Minimize Drug-Related Risks.

We will screen very carefully for alcohol use and depressive symptoms. It will be made explicit that participants are not to drink alcohol in evening. We will use the Alcohol Use Disorders Identification Test (AUDIT) score and our mental health counselors SCID-screeners to enroll only those with low risk for alcohol abuse. Subjects will report no current depressive symptomatology (Beck Depression

Inventory, or BDI < 15), with no past depressive episodes or suicidal ideation. The Columbia Suicide Severity Rating Scale (CSSRS) will be administered at each visit (see additional details below), as per NIH/FDA guidelines. Indication of regular alcohol use by AUDIT score, intake self-report, or breath alcohol, or indication of increase in depressive symptomatology / suicidality as measured by the CSSRS will result in study stopping (see details below). Will exclude for any patients taking CYP3A inhibitors; patients with severe hepatic impairment; and women who are or become pregnant. Pregnancy and drug tests are administered on via urinalysis on lab testing days. Women of childbearing capacity must be taking one form of birth control. We will exclude for women with BMI > 30 to decrease risk of side effects, although it should be noted that in our cocaine use disorder population, we rarely encounter obese patients.

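### The alcohol exclusion differs between sections: an ambiguous 'and' ties willingness to stop evening drinking to the weekly limit, and numbered criterion 12 contains neither willingness nor binge drinking

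*Combined protocol and SAP*

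**What the plan says.** Alcohol eligibility is described in four parts of the document.

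- **Research Plan, 'Participants and setting'.** Alcohol use disorder is excluded. The plan will also "exclude those individuals who are drinking > 10 alcoholic drinks per week", a clause that continues "and who are unwilling to stop using alcohol in the evening for the two weeks of the study". A separate sentence adds: "We will exclude those who report binge drinking", defined as 5 drinks for men or 4 for women in under 2.5 hours.
- **E1, opening paragraph.** Alcohol use disorder is excluded, and the study will "exclude those individuals who are drinking > 7 alcoholic drinks per week, and who are unwilling to stop using alcohol in the evening". Binge drinking is not mentioned.
- **E1, numbered exclusion list, item 12.** The whole alcohol criterion is "subjects with alcohol use disorders or are drinking > 7 alcoholic drinks per week". It says nothing on willingness or binge drinking.
- **E4, 'Procedures to Minimize Drug-Related Risks'.** "It will be made explicit that participants are not to drink alcohol in evening". AUDIT and SCID screening is meant to "enroll only those with low risk for alcohol abuse", and an indication of regular alcohol use leads to study stopping. No AUDIT cut-off is given and 'regular' is not defined.

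E10 repeats the limit of 7 drinks a week without a willingness condition. It also names E1 as the place where subject selection is described.

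**The concern.** Dosing is at 10 PM. The protocol gives its reason for the alcohol rules: it regards the drug as contraindicated with alcohol, and E10 calls the sedative interaction potentially dangerous. Willingness to stop evening drinking and a binge pattern are the conditions closest to that exposure. Neither is in the numbered list, which screening staff are likely to work from.

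The prose does not settle the matter, because its 'and' can be read in two ways. It may require both conditions for exclusion, or it may name two groups who are each excluded. Two screeners following different sections, or reading the same sentence differently, could decide differently on the same applicant.

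**Working it through.** No sample-size or power figure enters here, so the check is to apply each written rule to each type of applicant. All cases assume no alcohol use disorder.

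**Rules**
- A, 'Participants and setting': more than 10 a week 'and' unwilling; separately, binge drinking.
- B, E1 opening paragraph: more than 7 a week 'and' unwilling.
- C, criterion 12: more than 7 a week.

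**Is the applicant excluded?** 'Literal' means both conditions are needed. 'Two groups' means either is enough.

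| Applicant | A literal | B literal | A two groups | B two groups | C |
|---|---|---|---|---|---|
| 1. At most 7, unwilling, no binge | no | no | yes | yes | no |
| 2. At most 7, willing, binge | yes | no | yes | no | no |
| 3. 8–10, willing, no binge | no | no | no | yes | yes |
| 4. 8–10, unwilling, no binge | no | yes | yes | yes | yes |
| 5. Over 10, willing, no binge | no | no | yes | yes | yes |

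**Reading the table**
- Row 1: on the literal reading no listed criterion excludes this person. On the two-group reading A and B do, but criterion 12 does not.
- Row 2: the binge exclusion exists only in A. The reading of 'and' makes no difference.
- Rows 3 to 5: on the literal reading A conflicts with criterion 12 in all three rows, and B does so in rows 3 and 5. On the two-group reading only row 3 is left, and it comes from the 10 versus 7 limit.
- Neither reading makes the three texts agree.

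**Bounds for an individual**
- Row 1: at most 7 drinks/week × 2 weeks = 14 drinks over the 14 dosing days.
- Row 2: one weekly occasion of 5–7 drinks (men) or 4–7 (women) within 2.5 hours, with a weekly total of at most 7, is a binge under A but not over 7 under C. Over two weeks that is 1 × 2 = 2 occasions.

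**Monitoring after enrollment.** Breath alcohol is tested on arrival, and visits are at 10 AM, 12 hours after the 10 PM dose. Of the 7 visits, the first precedes dosing, so 7 − 1 = 6 follow a dosing night: at most 6 of 14 nights have a next-morning test. Whether that test would show light drinking the evening before is not addressed.

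**The case against.** A reader might infer that lighter drinkers who refuse to stop, and binge drinkers, can simply be enrolled and dosed because they pass every written alcohol limit. The documents do not support that.

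- 'Participants and setting' excludes binge drinking outright. The defect is that E1 omits it, not that the protocol permits it.
- The comma and the repeated relative clause allow the two-group reading, under which both prose sections exclude the unwilling light drinker. Criterion 12 and E10 apply the limit of 7 with no willingness condition, which favours that reading.
- E4 screens for low alcohol risk and stops participation on regular use, using AUDIT, intake self-report or breath alcohol. Neither rule depends on the weekly limit. One drink every evening would be hard to describe as anything but regular.
- The numbered list is not worded as closed. Other exclusions, such as that for women with BMI over 30, appear only in E4. E10 points to E1, E4 and E9, and to application sections not available here, for medical and psychological screening.

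These points rule out the stronger reading but do not close the gap. The E4 instruction not to drink in the evening is not an eligibility test for someone who has already said they will not comply. The E4 screen has no cut-off and 'regular' is undefined. The nearest figure, E10's account of frequent consumption, is again more than 7 a week, so it does not clearly reach lighter drinkers. Criterion 12 still disagrees with the prose under either reading.

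A reader might also infer that evening alcohol would measurably blur the sleep mediator or the eye-tracking outcome. That is plausible, but the documents give no figure for it; they link alcohol to sedation and adverse-effect risk.

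**Conclusion.** The concern holds as an inconsistency in a safety-based eligibility rule. Two conditions the sponsor wrote, on evening drinking and on bingeing, are missing from the numbered criterion; one depends on an ambiguous conjunction and the other appears in a single section. Screening from criterion 12 alone would pass a weekly binge drinker whom 'Participants and setting' excludes. It would also pass an unwilling light drinker, whom the prose excludes only on the two-group reading; on the literal reading only the E4 screen might reach that person.

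The size cannot be estimated. The 14 drinks and 2 binge occasions are upper bounds for hypothetical individuals, the number of such applicants is not given, and some would be assigned placebo. The conclusion assumes that screening follows the written text and that the unavailable application sections do not resolve the matter. It takes no view on which clinical rule is right.

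**What to change.** Reconcile 'Participants and setting', the E1 opening paragraph, criterion 12, the E4 alcohol paragraph and the E10 restatement. Each should state the sponsor's intended conditions on weekly intake, willingness to stop evening alcohol and binge drinking in the same words, with no doubt whether each condition excludes alone or only in combination. Settle the 10 versus 7 weekly limit in the same edit, and define the AUDIT threshold and 'regular' use relied on in E4. Carry the result into the numbered exclusion list and the screening form. The choice of rule belongs to the sponsor.

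The cost is a short text amendment and an updated form, with possibly a few more screen failures.
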